## **11.0 STATISTICAL CONSIDERATIONS**

- 11.1 OVERVIEW: The primary objective of this prevention trial is to assess whether participants randomized to receive finasteride for seven years will have a different proportion of prostate cancer than participants randomized to receive a placebo for seven years. Other objectives of this study are listed in the Objectives section of this protocol (Section 1.0) and include estimation of the side-effect rates associated with finasteride, assessment of the acceptability of long-term finasteride use by healthy participants, and assessment of the effect of finasteride on the sensitivity and specificity of DRE and PSA.

A study of 18,000 randomized subjects (9,000 placebo, 9,000 finasteride) is planned. The trial will be double-blind. The participants to be enrolled will be 55 years old, generally healthy, have a normal PSA, and be free of significant chronic comorbid disease, especially severe symptoms of BPH.

The participants randomized will be scheduled for prostate biopsy following seven years of study treatment. The primary outcome is the presence or absence of prostate cancer as assessed by the end-of-study biopsy or prior to seven years on study.

It is projected that accrual will be completed in three years, with approximately 3,600 subjects (20%) randomized in the first year and approximately 7,200 subjects (40%) in each of years two and three. It follows that the last biopsy will be completed ten years following the beginning of enrollment.

The validity of this study depends on a number of CRITICAL ASSUMPTIONS related to the ability to know when a participant is not adherent, between arm comparability for the

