possible in the finasteride arm. Therefore the degree of medication adherence and contamination must be known when performing PSA assessments. The plan is to assess adherence/contamination prior to obtaining PSA specimens and to defer taking a PSA specimen in cases where there is evidence of nonadherence or contamination until there is sufficient adherence and lack of contamination. Thus, the participant is motivated to become adherent and not take open label finasteride. Also, meaningless PSA results are avoided. This strategy requires the following assumption, however:

**CRITICAL ASSUMPTION:** The procedures used to assess adherence in the individual participant at each visit where a PSA specimen is to be obtained are sufficiently sensitive and reliable to detect degrees of nonadherence affecting PSA level interpretation.

- 11.4 **SEVEN YEAR BIOPSY:** It is assumed that approximately 40% of the randomized participants will not have a prostate biopsy following seven years of study treatment and have not had a positive biopsy prior to seven years of treatment. Specifically, it is assumed there will be a 40% loss to biopsy based on the sum of 20% mortality, 15% lost to follow-up, and 5% biopsy refusals. The 20% mortality is based on an assumption that the median age at study entry will be 63 years, with the seven year U.S. (white) all-causes mortality for men that age assumed to be approximately 20%. The 15% lost to follow-up is based on experience with other prevention trials. The 5% biopsy refusal rate is based on the belief that participants who stay on the study drug for seven years will be motivated to find out whether or not they have prostate cancer.

**CRITICAL ASSUMPTION:** It is assumed that the factors affecting loss to biopsy will operate the same in both arms of the study so that the groups of participants who do not have biopsies (deaths, lost, refusal) will be comparable between the arms.

Conformity to the above assumption can be monitored by comparing between the arms the characteristics of the participants who do not have the seven year biopsy and the reason for not having the biopsy.

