placebo	side-effect percents		power
	placebo	finasteride	
1	1	2	.50
	1	3	.97
	1	4	.99
2	2	4	.86
	2	5	.99
	2	6	.99
5	5	8	.90
	5	10	.99
10	10	13	.67
	10	15	.99

11.12 CARDIOVASCULAR DISEASE: Because cardiovascular disease is common among the men of age 55 (eligibility ages of the participants to be enrolled) the power will be high to detect even small differences between the arms with respect to cardiovascular disease

incidence and events. For example, if the incidence rate for coronary artery disease (CAD) for participants on this study is estimated to be 25 per 1000 per year then there could be as many as 1575 diagnoses of CAD in the placebo arm, that is, 17.5% of the placebo arm participants. The 0.05 one-sided power to detect a 10% higher incidence of CAD in the finasteride arm (1733 incident cases or 19.3%) would be 91.4%.

- 11.13 **DATA AND SAFETY MONITORING:** An external Data and Safety Monitoring Committee (DSMC) will review the safety, mortality, side-effects, adherence, and potential violation of the assumptions necessary for trial validity. The DSMC will review unblinded trial monitoring data every six months.

The Data and Safety Monitoring Committee (DSMC) will be an independent panel of urologists, statisticians, epidemiologists, and ethicists (approximately 10 total members). PCPT Study Investigators will be excluded from membership in this committee, but may participate in the review of blinded data as necessary.

The DSMC will be provided with detailed reports of all adverse events and deaths, including summaries of hospitalization discharges and deaths.

Side-effect data will be monitored more closely for the first cohort of 3600 subjects than for those who follow. The purpose of this monitoring will be to confirm previous finasteride studies which claimed minimal side-effects. Adherence data will be reviewed in order to provide the opportunity to implement additional adherence measures.

A monitoring system for detecting deviations from the CRITICAL ASSUMPTIONS will be active throughout the trial. This system will be used to generate data for DSMC review. Because of the fragility of this trial with respect to conformity to CRITICAL ASSUMPTIONS, and the resulting complexity of the monitoring tasks, no specific stopping rules are specified.

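### The 91.4% power for coronary artery disease assumes every randomized man is at risk for seven full years; the plan's own mortality and loss assumptions bring it to about 84-85%

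*Supplement*

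**What the plan says.** Section 11.1 sets the size: "A study of 18,000 randomized subjects (9,000 placebo, 9,000 finasteride) is planned". Section 11.12 says that power will be high for even small cardiovascular differences and gives an example. The coronary artery disease (CAD) incidence rate "is estimated to be 25 per 1000 per year", from which "there could be as many as 1575 diagnoses of CAD in the placebo arm, that is, 17.5% of the placebo arm participants" follows in the text as the placebo expectation. The alternative and its power come in one sentence: "The 0.05 one-sided power to detect a 10% higher incidence of CAD in the finasteride arm (1733 incident cases or 19.3%) would be 91.4" per cent. Section 11.12 mentions no allowance for death or loss.

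Section 11.4, on the seven-year biopsy, budgets a 40% loss as "the sum of 20% mortality, 15% lost to follow-up, and 5% biopsy refusals". Sections 11.9 and 11.10 carry attrition (60% biopsied), contamination and nonadherence into the power for the primary outcome.

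**The concern.** The CAD case count is rate times seven years times everyone randomized. No man dies, is lost, or leaves the risk set during that time. The same statistical section expects 20% of men to die and 15% to be lost over those seven years, and its primary power calculation allows for attrition. The CAD calculation does not, and does not say so.

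This is the only power the plan states for cardiovascular harm, in a seven-year trial of healthy men. If CAD incidence turned out similar in the two arms, a reader could take that as reassurance backed by 91% power against a 10% increase. Under the plan's own attrition the chance of missing such an increase is about 15-16% on the linear count, against the 9% implied.

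**Working it through.** **Inputs.** 9,000 men per arm (11.1); 25 per 1000 per year, a 10% relative increase, one-sided 0.05 (11.12); 20% mortality and 15% loss to follow-up over seven years (11.4). The 5% biopsy refusals are left out because refusing a biopsy does not remove a man from CAD reporting. Assumptions not in the protocol: when deaths and losses occur, and that CAD follow-up stops at death or loss.

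**Formula.** Two-proportion normal approximation with continuity correction, n = 9,000 per arm, p̄ = (p0 + p1)/2:

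power = Φ{ [ |p1 − p0| − 1/n − 1.645·√(2p̄(1−p̄)/n) ] / √([p0(1−p0) + p1(1−p1)]/n) }

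**1. Reproduce the printed figure.**
- Placebo cases: 9,000 x 7 x 0.025 = 1,575, so p0 = 0.175. Finasteride: 1,575 x 1.10 = 1,732.5, so p1 = 0.1925 (printed as 1,733 and 19.3%).
- The difference is 0.0175, and both standard errors are about 0.00577. z = (0.0175 − 0.00011 − 1.645 x 0.00577)/0.00577 = 1.367, so power = 0.914.
- Without the continuity correction it is 0.917. The printed 91.4% is therefore the continuity-corrected value with full follow-up.

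**2. Linear count with 35% attrition, spread evenly.**
- Person-time kept: 1 − 0.35/2 = 0.825.
- p0 = 0.175 x 0.825 = 0.1444 (about 1,299 cases); p1 = 0.1925 x 0.825 = 0.1588.
- Difference 0.01444, standard error about 0.00535, z = 1.035, power 0.850 (0.855 without the correction).

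**3. Linear count with 35% attrition as a constant hazard.**
- Hazard = −ln(0.65)/7 = 0.0615 per year. Person-years per man = 0.35/0.0615 = 5.687, or about 51,186 per arm (81% kept).
- Cases: 51,186 x 0.025 = 1,280 against 51,186 x 0.0275 = 1,408; power 0.844 (0.849 uncorrected).

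**4. Mortality alone (20%), linear, even.** Person-time kept 0.90; 15.75% vs 17.33%; power 0.881 (0.885 uncorrected).

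**5. If 25 per 1000 is a first-event hazard.** Risk over seven years with attrition hazard μ is h/(h+μ) x (1 − e^(−7(h+μ))).
- With μ = 0.0615: 13.13% vs 14.32%, that is 1,181 vs 1,289 cases; power 0.749 (0.756 uncorrected).
- With no attrition at all: 16.05% vs 17.51%; power 0.829 (0.834 uncorrected).

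**6. Increase detectable at 90% on the linear count with full attrition.** A relative increase of 11% gives 0.903 with even timing and 0.898 with constant-hazard timing.

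**7. Sensitivity only.** Carrying 5% contamination and 10% nonadherence into steps 2 and 3 gives about 0.73-0.74.

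**The case against.** The strongest reply is that nothing has been miscalculated and that the passage is a conditional, upper-limit illustration: "there could be as many as 1575 diagnoses of CAD in the placebo arm" is hedged, the rate is introduced hypothetically, and no sample size, analysis or stopping rule depends on it. That stands as far as it goes. It settles that this is a question of inputs. It does not cover the power sentence, which gives one value with no range and does not say that an upper-limit count yields an upper-limit power.

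A second reply concerns the attrition. The Cardiovascular Assessments part of the Background links about half of deaths at this age to cardiovascular disease, so some assumed deaths would themselves be CAD cases. The 15% loss is also budgeted in 11.4 for the biopsy, not for CAD reports. Both points have force. If, for illustration, half the deaths were not competing, attrition would be 25% and the linear count would give about 87%. Attrition late in follow-up would also cost less power than the timings used here.

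Third, 11.12 speaks of cardiovascular disease generally. The Background expects it three to five times as often as prostate cancer; with the plan's 6%, that is loosely 18-30%. On those inputs a 10% relative increase keeps about 86-98% power with 82.5% of person-time. The general statement that power is high largely survives. The data and safety monitoring committee also reviews unblinded safety data every six months, so protection against harm does not rest on this number.

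A reader might go further and infer that true power is only about 59-74%, by applying contamination and nonadherence. The documents do not support presenting that as the plan's own figure. Section 11.7 defines those degrees for men who have prostate cancer at the end of the study, 11.1 ties the 10% and 5% limits to the primary power, and the 14% in 11.10 is one primary-outcome scenario. The CAD alternative also reads naturally as a difference between arms as randomized, which would need no further dilution.

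**Conclusion.** The point holds in a limited form. The 91.4% is a full-follow-up value that 11.4's assumptions do not deliver. On the plan's own linear count, the loss is about 3 points for mortality alone (to about 88%) and 6-7 points for mortality plus loss to follow-up (to about 84-85%, with about 1,280-1,300 placebo cases). These rest on even or constant-hazard timing, and on treating every death and loss as ending CAD follow-up.

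A reader might infer a much larger shortfall from the first-event figure of about 75%. That depends on reading 25 per 1000 as a hazard among men still free of CAD, which the protocol does not state, so it is a conditional result and not the headline. The primary outcome and the trial's size are unaffected.

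**What to change.** Restate the example in 11.12 with the 11.4 attrition: about 1,280-1,300 placebo cases and about 84-85% power, or about 75% if the rate is meant as a first-event hazard. Say which kind of rate it is and name the timing assumption. Alternatively, state that about an 11% relative increase is detectable at 90% power on the linear count. Either way, label 91.4% as an upper bound under complete seven-year follow-up. If a figure diluted for contamination and nonadherence is added, mark it as a sensitivity value borrowed from the prostate cancer outcome.

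This changes wording only, with no effect on design, conduct or analysis. The one downside is that a stated power becomes less favourable.

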### Secondary Objectives

- 1.2 To assess the effect of finasteride on the stage and grade of carcinoma of the prostate at the time of diagnosis.
- 1.3 To assess the toxicity and side effects of finasteride when administered on a long-term basis.
- 1.4 To estimate the difference in the total and prostate-cancer specific mortality between men treated with finasteride and those treated with placebo.
- 1.5 To estimate the difference in incidence and severity of benign prostatic hyperplasia between men treated with finasteride and those treated with placebo.
- 1.6 To estimate the sensitivity, specificity and predictive values of digital rectal examination (DRE), PSA (Prostate Specific Antigen) and PSA + DRE as screening tests for the detection of prostate cancer, and to estimate the effect of long-term finasteride treatment on these screening parameters.
- 1.7 To assess the effect of long-term treatment with finasteride on the participants' self-report of urinary and sexual function symptoms and other Quality of Life dimensions.
- 1.8 To investigate whether dietary fat, assessed as intake of total fat, saturated fat and high fat foods, is associated with increased risk of prostate cancer (see Appendix 19.7 for related aims).
- 1.9 To assess the degree to which CAG trinucleotide repeat length is associated with an increased risk of prostate cancer (see Appendix 19.8 for related aims).

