participants who do not have a seven year biopsy, the mathematical form of the relationship of finasteride's effect on PSA levels, finasteride's effect on DRE and TRUS sensitivity, and the size of finasteride's effect in preventing BPH. (The CRITICAL ASSUMPTIONS are identified and discussed subsequently.) These CRITICAL ASSUMPTIONS are necessary because of finasteride's effect on the size of the prostate gland and particularly the tendency for finasteride to reduce PSA levels. The consequences of finasteride's effect on PSA are magnified by PSA's growing importance as a marker for prostate cancer incidence. In general terms, the intervention under study affects an important diagnostic test for the detection of the disease under study. These CRITICAL ASSUMPTIONS are necessary despite the design compromises made to accommodate finasteride's effect on PSA as described in the Background section of this protocol (Section 2.0).

The study is planned for a 5% two-sided test and will have 90% or greater power to detect a 25% difference between the arms in the proportion of prostate cancers following seven years of study treatment. This power computation is based on the following parameters: the non-adherence in the finasteride arm does not exceed 10%, the placebo arm finasteride use does not exceed 5%, and at least 60% of the participants have the seven year biopsy. The anticipated loss of participants is due to refusal, loss to follow-up, or death.

There will be no interim analysis of the primary outcome because the primary outcome will not be known until the end of the study. There will be close monitoring of the study with respect to safety, mortality, side-effects, conformity to the trial planning parameters, and conformity to the CRITICAL ASSUMPTIONS.

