- 11.7 **ADHERENCE:** A three month enrollment period during which each participant is to take study medication (in this case placebo) is part of the design. Following the enrollment period medication adherence will be assessed and only participants with sufficient adherence will be randomized. The degree of "placebo effect" will also be assessed and be a basis for exclusion from randomization.

For participants who have a prostate cancer at the end of the study it is assumed that the degree of placebo arm finasteride contamination, designated  $d_0$ , will be approximately 0.05 (zero implies no contamination, one implies 100% contamination) and the degree of finasteride arm nonadherence, designated  $d_1$ , will be approximately 0.10 (zero implies complete adherence and one implies 100% nonadherence). These degrees of contamination and adherence ( $d_0$  and  $d_1$ ) are used as follows. Let  $p_0$  and  $p_1$  be the true prostate cancer probabilities for the placebo arm and finasteride arms, respectively. The seven year prostate cancer probabilities adjusted for the assumed adherence and contamination are  $p_{0r} = ((1 - d_0) \times p_0 + d_0 \times p_1)$  and  $p_{1r} = (d_1 \times p_0 + (1 - d_1) \times p_1)$  for the placebo and finasteride arms, respectively.

[figure not shown]
- 11.8 **PROBABILITY ASSUMPTIONS:** The true probability of detectable prostate cancer in the placebo group at seven years following study entry ( $p_0$ ) is assumed to be in the neighborhood of 6% (24,25).

The probability difference for seven years of treatment is defined as the difference of the true probability of prostate cancer at seven years in the finasteride arm minus the true probability of prostate cancer at seven years in the placebo arm, or  $p_1 - p_0$  (NB: a negative difference implies a finasteride benefit). This difference is can be multiplied by 100 and divided by  $p_0$ , that is  $100 \times (p_1 - p_0) / p_0$ , to give the percent difference due to finasteride. The probability difference adjusted for the assumed degrees of placebo arm contamination and finasteride arm nonadherence is  $p_{1r} - p_{0r}$  and this difference is also can be used as the adjusted percent difference due to finasteride, or  $100 \times (p_{1r} - p_{0r}) / p_{0r}$ .

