- 11.9 **PRIMARY ANALYSIS:** The primary outcome analysis will consist of testing the coefficient of the arm indicator variable in a logistic regression model for the probability of prostate cancer. The logistic regression model will include covariates for all stratification factors except the Study Center. This analysis will include all subjects who have a biopsy at seven years plus the subjects who were found to have prostate cancer (histologically-proven) prior to seven years. The power computations which follow use standard formulas for computing the power when comparing proportions. The actual power of the trial is computed based on  $p_{0r}$  and  $p_{1r}$ , the probabilities adjusted for assumed degrees of contamination and nonadherence.

- 11.10 **POWER:** Based on 9,000 participants per arm, the graphs in Figure 4 illustrate actual power for an assumption of 60% of participants biopsied, true probability of prostate cancer in the placebo arm ( $p_0$ ) of 4% and 6%, unadjusted percent differences of 25% and 30%, and ranges for degrees of placebo arm contamination and finasteride arm nonadherence as described previously. If the desired actual power is 90% or above then the graphs in Figure 4 illustrate that this power is achievable provided: the unadjusted percent difference is 30%, the true probability of a positive biopsy in the placebo group ( $p_0$ ) is close to 6%, and the degree of placebo arm contamination and finasteride arm nonadherence do not become excessive. There is much less latitude for an unadjusted percent difference of 25%.

In particular, using the 60% biopsy rate, the power is 92.1% for an adjusted difference of 24.7% from a 6% placebo arm prostate cancer rate using a 5% placebo group contamination and a 14% finasteride arm nonadherence. This power computation is labeled in the fourth graph in Figure 4. These conditions are believed to be achievable if the trial is tightly controlled.

11.11 POWER FOR SIDE-EFFECTS AND ADVERSE EVENTS: The reported experience for one year of treatment with placebo (n=300) versus finasteride 5 mg (n=300) by the manufacturer includes the following:

	Finasteride	Placebo
decreased libido	4.7%	1.3%
ejaculatory disorder	4.4%	1.7%
impotence	3.4%	1.7%

The power using the first 1800 subjects per arm to detect differences in these measures (including a combined measure of sexual dysfunction) is shown below. The 1% one sided alpha level is used to permit five multiple comparisons at the 5% level.

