- 11.14 **SECONDARY ANALYSES AND SECONDARY OBJECTIVES:** Beyond the analysis of the primary outcome described above, the probability of prostate cancer at seven years will be modeled using standard methods for categorical data, with explanatory variables including age, race, family history, gland size, laboratory data, etc. The probability of side-effects will be modeled using information on adherence (and other covariates).

Objective 1.2 (finasteride's effect on stage and grade) will be analyzed by comparing between the arms the grade and stage distribution of the incident cases. Data will come from pathology review of biopsy specimens. Standard categorical data analysis methods will be used.

Objectives 1.3, 1.4, 1.5, and 1.7 (toxicity, side-effects, mortality, BPH, and quality of life) will be analyzed by comparing between the arms the rates of events and magnitudes of effects. The data will come from reports of events, participant interviews, and side-effect and quality of life questionnaires. Standard categorical data methods, including methods for ordered categorical data will be used.

Objective 1.6 (finasteride's effect on screening modality) will require detailed pathology data as well as an analysis of the data generated from the procedures used to adjust PSA levels. Should finasteride prove to be efficacious in preventing prostate cancer then it will be important to be able to recommend to practitioners methods for monitoring for prostate cancer in those taking finasteride. Additional data addressing this issue may become available from trials of the use of finasteride in BPH.

Objective 1.8 (association of dietary fat and an increased risk of prostate cancer) will be approached as detailed in Appendix 19.7, which outlines methods of data collection and analysis.

Objective 1.9 (cohort study of CAG repeat length) will be approached as detailed in Appendix 19.8.

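### Objective 1.2 is analysed only among men who became cases, so a fall in low-grade cancer can look like a harmful grade effect and a real fall in high-grade cancer can be hidden

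*Supplement*

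**What the plan says.** The objective, in the protocol's Section 1.0, is "To assess the effect of finasteride on the stage and grade of carcinoma of the prostate at the time of diagnosis". That is a question about an effect of treatment.

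Section 11.14 answers it in one way: it "will be analyzed by comparing between the arms the grade and stage distribution of the incident cases". On method it adds only: "Data will come from pathology review of biopsy specimens. Standard categorical data analysis methods will be used". It gives no grade cut-point and no stage grouping.

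The primary analysis in Section 11.9 uses a wider set of men: "This analysis will include all subjects who have a biopsy at seven years plus the subjects who were found to have prostate cancer" before that time. Its outcome is any prostate cancer. The further seven-year model in Section 11.14 and the life table in Appendix 19.10 (Section 5.0, Incidence) also use any cancer. None is split by grade or stage, and no section warns about comparing arms within a group defined by having developed cancer.

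**The concern.** Randomisation makes the arms comparable among all men, not among those who later have cancer. If the drug prevents some cancers, the finasteride cases are what remains after that prevention. Their grade mix then reflects which tumours were removed as well as any change in the tumours left.

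The same high-grade share among cases can therefore go with fewer, equal or more high-grade cancers. In healthy men this distinction decides how a fall in total incidence should be read. The design discussion in Section 2.0 itself notes that many detectable tumours never cause harm.

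Unequal prevention by grade is possible on the protocol's own rationale. Section 2.0 reports a higher DHT/DNA ratio in better-differentiated tumours, though it does not quantify any selectivity. Section 7.14d commits the trial to intention-to-treat analysis, and Section 11.14 compares event rates between arms for toxicity, mortality and BPH. Objective 1.2 is the exception.

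**Working it through.** **Inputs from the plan.** Section 11.1: "The study is planned for a 5% two-sided test"; "A study of 18,000 randomized subjects (9,000 placebo, 9,000 finasteride) is planned"; and "at least 60% of the participants have the seven year biopsy". That gives n = 0.60 × 9,000 = 5,400 evaluable men per arm. Section 11.8: the placebo probability "is assumed to be in the neighborhood of 6" per cent. Section 11.10: a 30% unadjusted reduction, 5% contamination, 14% nonadherence, an adjusted difference of 24.7% and power of 92.1%.

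**Input not in the plan.** The placebo high-grade share f is assumed, over 10% to 50%.

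**1. Reproducing the plan's power.**
- p0r = 0.95 × 0.06 + 0.05 × 0.042 = 0.0591
- p1r = 0.14 × 0.06 + 0.86 × 0.042 = 0.04452
- Adjusted difference = (0.04452 − 0.0591)/0.0591 = −24.7%
- Power at n = 5,400, two-sided 5%: 92.2% with continuity correction, 92.8% without. The stated 92.1% is reproduced.

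**2. Expected cases (placebo vs finasteride).**
- Section 11.10 scenario: 5,400 × 0.0591 = 319 vs 5,400 × 0.04452 = 240
- Undiluted 25% reduction: 5,400 × 0.06 = 324 vs 5,400 × 0.045 = 243
- Diluted 25% reduction (5% contamination, 10% nonadherence): 5,400 × 0.05925 = 320 vs 5,400 × 0.0465 = 251

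**3. All prevention falls on low-grade tumours.** High-grade counts are equal, so the high-grade share among cases is multiplied by the ratio of case counts: 324/243 = 1.33, and 319/240 = 1.33.

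Example with 324 vs 243 and f = 25%: 81 high-grade cancers in each arm.
- Case-only: 81/324 = 25.0% vs 81/243 = 33.3%
- Pooled share = 162/567 = 0.2857
- z = 0.0833/√[0.2857 × 0.7143 × (1/324 + 1/243)] = 2.17, p = 0.03
- Chance that the test declares worse grade = Φ(2.17 − 1.96) ≈ 58%
- All evaluable men: 81/5,400 = 1.5% in both arms

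With the diluted counts (320 vs 251) and f = 25%: 25% vs 31.9%, z = 1.81, p = 0.07, chance Φ(1.81 − 1.96) ≈ 44%.

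Simulation of the Section 11.10 scenario (319 vs 240; 40,000 trials):

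| Assumed placebo share | Finasteride share | Odds ratio among cases | Case-only test says worse | All evaluable men, test says worse |
|---|---|---|---|---|
| 10% | 13.3% | 1.38 | 23% | 2.5% |
| 20% | 26.5% | 1.45 | 45% | 2.5% |
| 30% | 39.8% | 1.54 | 68% | 2.4% |
| 40% | 53.1% | 1.70 | 87% | 2.6% |
| 50% | 66.4% | 1.97 | 98% | 2.5% |

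With the diluted counts the same range of shares gives lower figures: Φ(1.03 − 1.96) = 18% at f = 10%, and Φ(3.28 − 1.96) = 91% at f = 50%.

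**4. A true benefit on high grade.** If finasteride also cuts high-grade cancer by 10%, with 319 vs 240 cases in total, the case-only test still declares worse grade in 11% to 63% of trials. With all evaluable men as denominator the figure is under 1%.

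**5. Proportional prevention.** With 324 vs 243 cases and f = 25% in both arms, high-grade cancers fall from 81 to 61 (0.25 × 243), while the case-only comparison is 25% vs 25%. In simulation of the Section 11.10 scenario it keeps its 5% level. A test on all evaluable men detects the fall in 32% (f = 20%) or 46% (f = 30%) of trials.

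**6. More than two grade categories.** Holding the shift in step 3 at z² = 4.73 and testing it with a general chi-square gives rejection rates of about 48% (2 df), 38% (4 df) and 28% (8 df).

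**The case against.** Grade at diagnosis exists only for men with a diagnosis, so a table of case mix follows the objective's literal wording and is a sound description of the tumours found. That stands. The fault arises when a difference in that table is tested and read as an effect of finasteride, which is how Objective 1.2 is phrased.

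A reader might infer that the analysis is bound to show worse grade on finasteride. The documents do not support that. The plan assumes one effect on any cancer and no selectivity by grade. Under proportional prevention the case-only test holds its level. Under low-grade-only prevention the expected shift in share is certain, but significance is not.

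A reader might also infer that the trial could not answer the question at all. That goes too far: high-grade counts by arm and the Section 11.9 denominators would both be available. What is missing is a stated analysis that uses them. Only a protocol is shown, and detail such as cut-points could be left to a separate analysis plan. The choice of cases as the comparison group, however, is made in Section 11.14 itself.

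The alternative denominator is not clean either. The Section 11.9 set leaves out the roughly 40% expected to have no endpoint (Section 11.4), so it too is selected after randomisation. Appendix 19.10 warns that smaller treated glands may be oversampled at biopsy, which could raise detected high-grade cancer on finasteride under any denominator. Both limits stand, and the case-only comparison shares them.

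**Conclusion.** The concern holds in conditional form. Section 11.14 tests a causal objective within a group that treatment is expected to alter, and no other planned analysis supplies the missing comparison.

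If prevention falls only on low-grade tumours, the high-grade share among cases rises by about one third at the plan's rates. A false finding of worse grade then follows in roughly 23% to 98% of trials. That range rests on an assumed high-grade share of 10% to 50% and a two-category test; it is lower with diluted counts or more grade categories. Partial selectivity gives a smaller distortion in the same direction. If prevention is equal across grades, the error is the reverse: a real fall in high-grade cancer does not show. The direction of these distortions is arithmetic and applies to stage as well; the percentages depend on the assumptions. The primary analysis is not affected.

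**What to change.** In Section 11.14, make the main analysis for Objective 1.2 the comparison between arms of the risk of high-grade cancer, of low-grade cancer and of each stage group, with all men in the Section 11.9 population as denominator. Multinomial logistic regression (no cancer, low grade, high grade) with the Section 11.9 covariates would do this, with a parallel model for stage. State the grade cut-point and stage groups in advance.

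Add a sensitivity analysis with all randomised men as denominator. Keep the case-only distribution as description, labelled as a non-randomised comparison. State that the Section 11.9 set excludes the roughly 40% without an endpoint and that neither denominator removes differential detection.

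The cost is analysis wording. Central pathology review and the outcome data are already planned, so no new data are needed.
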